5.3 Removal of Subjects from Study Therapy or Assessment

Subjects may choose to discontinue the study at any time, for any reason, and without prejudice to further treatment.

Subjects may stop participating in or be withdrawn from the study for any of the following reasons but are to be followed for safety until resolution or for 14 days after the subject's last study visit, whichever comes first (see Section 10.1.5):

- Lack of efficacy
- Occurrence of an unacceptable AE
- Opioid withdrawal
- Noncompliance of the subject with protocol-mandated procedures
- Continued participation is no longer in the subject's best interest in the opinion of the Investigator
- The subject is lost to follow-up. Before a subject is considered "lost to follow-up," study personnel must contact the subject at least twice by phone and once by mail with documented receipt(s)
- Death
- The study is terminated by the sponsor

During the treatment period, if an ECG is obtained and reveals that the subject's QTcF interval is > 500 msec or has an increase of ≥ 60 msec compared to baseline QTcF and confirmed with a second ECG within 30 minutes, treatment with study medication should be interrupted. In the event this occurs, the investigator should contact the Medical Monitor as soon as possible to discuss if the subject can continue on treatment or if the subject should stop study medication.

In the event of a subject's withdrawal, the Investigator will promptly notify the sponsor and make every effort to complete the ET assessments specified in the Schedule of Assessments (Section 1.2).

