10.1.6 Serious Adverse Event Definition

An SAE is defined as any untoward medical occurrence that at any dose:

- Results in death;
- Is life-threatening, i.e., in the opinion of the Investigator or sponsor, the AE places the subject at immediate risk of death from the event as it occurred; it does not include a reaction that, had it occurred in a more severe form, might have caused death;
- Requires inpatient hospitalization or prolongation of an existing hospitalization that occurs during the course of a subject's participation in a clinical study, except for those that occur due to any of the following:
 - A surgery or procedure that was planned or anticipated before the subject entered the study and that is part of the planned study procedure; or
 - Nonmedical reasons, in the absence of an AE;
- Results in persistent or significant disability or incapacity;
- Is a congenital anomaly or birth defect; or
- Is an important medical event that, based upon appropriate medical judgment, may jeopardize the subject and may require medical or surgical intervention to prevent one of the other outcomes listed above.

Death is an outcome of an AE, and not an AE in itself. All fatal events regardless of causality must be reported. "Life-threatening" means that the subject was at immediate risk of death from the event as it occurred. This does not include an event that might have led to death, if it had occurred with greater severity. "Inpatient hospitalization" means that the subject has been admitted to a hospital for medical reasons for any length of time. The Investigator should attempt to establish a diagnosis of the event based on signs, symptoms, and/or other clinical information. In such cases, the diagnosis should be documented as the AE and/or SAE and not the individual signs/symptoms.

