8.7.1 Adverse events

A treatment-emergent adverse event (TEAE) is defined as an event that first occurred or worsened in severity after the first administration of study drug (Visit 3) but on or prior to the end of study. Adverse events will be mapped to system organ class (SOC) and preferred term using MedDRA, version 17.1 or later.

The number and percent of subjects who had TEAEs, serious TEAEs, AEs with death outcome, AEs that led to study drug withdrawal, and AE of interest will be summarized. AE of interest is AEs which may indicate potential abuse. The list of abuse related AE of interest is in [Appendix 2](#) to [Appendix 4](#). For withdrawal symptoms (Error! Reference source not found.), only the preferred terms occurred after last dose of treatment will be considered as withdrawal. Adverse events will also be summarized by SOC and preferred term and presented by maximum reported intensity and by Investigator's causality assessment. Corresponding data listings will be presented as well.

An AE that was present at treatment initiation, but resolved and then reappeared while the subject was on treatment, is a TEAE (regardless of the intensity of the AE when the treatment was initiated). If the start date of an AE is incomplete and cannot be categorized as occurring before or after the first dose, then the AE will be considered as TEAE. If the start time of AE is provided then the AE start date and time will be used to classify the AE as TEAE or not. If the

start time is not provided and the AE occurs on the same day of first study drug administration then the AE will be classified as TEAE.

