8.7.2 Clinical and Subjective Opiate Withdrawal Scales

The COWS consists of 11 items to provide a description of the symptoms of withdrawal that can be directly observed by a physician interviewer: increased resting pulse rate, gastrointestinal upset, sweating, tremor, restlessness, yawning, pupil size, anxiety or irritability, arthralgias, piloerection of skin, and runny nose or tearing.

The total score of the COWS is the sum of the responses to the 11 items, which can range from 0 to 48, with higher scores indicating greater withdrawal severity. If there are missing items when the total score is calculated, the total score will be set to missing. Total score between 5 and 12 inclusive indicates mild withdrawal; between 13 and 24 inclusive indicates moderate withdrawal; between 25 and 36 inclusive indicates moderately severe withdrawal; and total score greater than 36 indicates severe withdrawal.

The SOWS is a self-rating scale which has been shown to be a reliable and valid measure of the opiate withdrawal syndrome. It contains 16 symptoms whose intensity the subject rates on a 5-point scale of 0 = not at all, 1 = a little, 2 = moderately, 3 = quite a bit, 4 = extremely. The total

score is a sum of item ratings, and ranges from 0 to 64. If there are missing items when the total score is calculated, the total score will be set to missing.

The total score for COWS and SOWS will be calculated at all scheduled assessment time points.

The COWS and SOWS total scores will be summarized descriptively. The total score of COWS will be summarized categorically by dose level.

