Nervous system disorders	Neurological disorders NEC	Paraesthesias and dysaesthesias	Hypoaesthesia
Psychiatric disorders	Disturbances in thinking and perception	Perception disturbances	Illusion
	Personality disorders and disturbances in behaviour	Behaviour and socialisation disturbances	Indifference
	Mood disorders and disturbances NEC	Emotional and mood disturbances NEC	Irritability
	Dementia and amnesic conditions	Amnesic symptoms	Memory impairment
	Cognitive and attention disorders and disturbances	Cognitive and attention disorders and disturbances NEC	Mental impairment
	Mood disorders and disturbances NEC	Fluctuating mood symptoms	Mood swings
Musculoskeletal and connective tissue disorders	Muscle disorders	Muscle tone abnormalities	Muscle rigidity
Psychiatric disorders	Sleep disorders and disturbances	Parasomnias	Nightmare
Nervous system disorders	Neurological disorders NEC	Paraesthesias and dysaesthesias	Paraesthesia
Psychiatric disorders	Personality disorders and disturbances in behaviour	Behaviour and socialisation disturbances	Paranoia

System Organ Class	Higher Level GT	Higher Level Term	Preferred term
	Schizophrenia and other psychotic disorders	Psychotic disorder NEC	Psychotic disorder
Nervous system disorders	Neurological disorders NEC	Sensory abnormalities NEC	Sensory disturbance
Psychiatric disorders	Disturbances in thinking and perception	Delusional symptoms	Somatic delusion
		Perception disturbances	Somatic hallucination
	Psychiatric and behavioural symptoms NEC	Abnormal behaviour NEC	Staring
	Sleep disorders and disturbances	Dyssomnias	Stupor
	Disturbances in thinking and perception	Thinking disturbances	Thinking abnormal
			Thought blocking
Schizophrenia and other psychotic disorders	Brief psychotic disorder	Transient psychosis	

***Drug Withdrawal- Related Adverse Events Occurring Following Drug Discontinuation
 (Preferred Terms; MedDRA 18.0)***

System Organ Class	Preferred term
Cardiac disorders	Syncope
Gastrointestinal disorders	Vomiting
	Diarrhoea
	Nausea
General disorders and administration site conditions	Hyperhidrosis
	Pain
Musculoskeletal and connective tissue disorders	Chills
Nervous system disorders	Headache
	Agitation
	Dyssomnia
	Insomnia
	Poor quality sleep
	Syncope
	Terminal insomnia (lower level term of interest: early morning awakening)
	Tremor
Psychiatric disorders	Agitation
	Anhedonia
	Anxiety
	Dysphoria
	Dyssomnia
	Dysthymic disorder
	Feeling of despair
	Insomnia
	Morose
	Negative thoughts
	Nervousness

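### The readable SAP withdrawal-AE list has no term for a withdrawal diagnosis, so a post-dose event recorded only as opioid withdrawal would be left out of that summary

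*SAP*

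**What the plan says.** SAP 8.7.1 summarises adverse events of interest, meaning those that may point to abuse, from term lists in the appendices. For withdrawal the pointer to the list is broken: "For withdrawal symptoms (Error! Reference source not found". The sentence goes on to say that "only the preferred terms occurred after last dose of treatment will be considered as withdrawal". The list meant is identifiable by its title, "Drug Withdrawal- Related Adverse Events Occurring Following Drug Discontinuation".

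Protocol 10.1.6 asks the investigator to try to reach a diagnosis and says that in such cases "the diagnosis should be documented as the AE and/or SAE and not the individual signs/symptoms". Protocol 5.3 names "Opioid withdrawal" among the reasons for which a subject may stop, and Protocol 6.2 and 10.10 provide for its treatment. The protocol thus treats withdrawal as a condition that sites will recognise and name.

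Withdrawal is also reported by other routes. SAP 5.0 makes COWS and SOWS the key safety measure of drug withdrawal. SAP 8.7.1 tabulates all adverse events by system organ class and preferred term. SAP 8.7.4 includes withdrawal among the event types that MADDERS classifies and adjudicates.

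**The concern.** The summary is defined by symptom-level terms, while the reporting instruction steers sites away from symptoms once a diagnosis is made. A site that follows Protocol 10.1.6 and writes opioid withdrawal as the event produces a record that matches no term in the readable list. The events most clearly identified as withdrawal would then be missing from the row labelled withdrawal, while non-specific single symptoms remain in it.

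For a new opioid, a reader may take that row as the withdrawal incidence from adverse-event reporting. Nothing in SAP 8.7.1 would tell that reader that diagnosed cases are excluded. Post-dose reports are foreseeable: under footnote 20 to the Schedule of Assessments, taper drug is not dispensed at early termination.

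**Working it through.** **1. Count the list.** Rows by system organ class as printed: Cardiac 1, Gastrointestinal 3, General 2, Musculoskeletal 1, Nervous system 8, Psychiatric 11. Sum: 1 + 3 + 2 + 1 + 8 + 11 = 26 rows. Four terms appear twice (Syncope, Agitation, Dyssomnia, Insomnia), so there are 26 − 4 = 22 distinct terms. Terms naming withdrawal, a withdrawal syndrome or dependence: 0 of 22. One term, "Dysthymic disorder", is a disorder and not a symptom, but it is a mood disorder and not a withdrawal diagnosis.

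**2. Check how far the list can be read.** The last visible entry is Nervousness, in the psychiatric block. That block is alphabetical, so a term beginning with Drug would stand before Dysphoria; it is not there. The general-disorders block is visible and holds only Hyperhidrosis and Pain. A term sorting after Nervousness, or a later organ-class block, could follow the visible text. The count therefore holds for the visible rows only.

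**3. Apply the rule to two example records.**

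| Record | On visible list? | After last dose? | Withdrawal summary |
|---|---|---|---|
| Opioid withdrawal, 2 days after last dose, no other listed event | No | Yes | 0 |
| Headache, 10 days after last dose | Yes | Yes | 1 |

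**4. Size, as illustration only.** The plan gives no figure to reproduce. Let W be the subjects with true post-dose withdrawal, f the share of them recorded only as the diagnosis and with no other listed post-dose event, and S the subjects without withdrawal who report a listed symptom after the last dose.

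- Subjects counted now = W(1 − f) + S
- Error against W = S − fW

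Take N = 600 (planned enrolment, Protocol 11.2) and S = 0. The incidences of 2% and 5% and all values of f are assumptions.

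| f | W = 600 × 0.02 = 12 | W = 600 × 0.05 = 30 |
|---|---|---|
| 0 | 12 | 30 |
| 0.25 | 9 | 22.5 |
| 0.50 | 6 | 15 |
| 0.75 | 3 | 7.5 |
| 1 | 0 | 0 |

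With a diagnosis term on the list and S = 0, the count is 12 or 30 at every f.

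**5. Net direction.** The error changes sign at S = fW. With W = 30 and f = 0.50 that is 15 subjects, or 15/600 = 2.5%. If more than 2.5% of subjects report an unrelated headache, nausea, insomnia or similar after the last dose, the row overstates withdrawal; if fewer, it understates it. The documents give none of W, f or S.

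**The case against.** The best case against the point has five parts.

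**The list is cut off.** The psychiatric block may well continue: Poor quality sleep and Terminal insomnia, both in the nervous-system block, would sort after Nervousness. A diagnosis term could be in the unseen rows. This stands, and it is why the point is conditional on a check of the full appendix.

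**The quoted sentence may only restrict timing.** It opens with withdrawal symptoms and can be read as saying that non-specific symptoms count only after the last dose. That is a fair reading, but the gap remains, because no other readable SAP text puts a withdrawal diagnosis into this category.

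**Diagnosed cases are reported elsewhere.** They have their own row in the preferred-term tables, MADDERS may capture them, and SAP 8.1 summarises reasons for stopping. This stands, and it limits the effect to one summary. A reader might infer that the trial's key withdrawal endpoint is compromised. The documents do not support that: the endpoint is COWS and SOWS, and neither depends on how adverse events are coded.

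**The supporting protocol text is soft.** The diagnosis instruction sits in the definition of serious events, and the investigator is asked only to attempt a diagnosis. It does apply expressly to non-serious events too. Protocol 5.3 shows only that withdrawal is a nameable condition: withdrawal that leads a subject to stop would usually begin before the last dose, and the timing rule would exclude it whatever the list holds.

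**The list need not copy COWS.** SAP 8.7.2 names the COWS signs as "increased resting pulse rate, gastrointestinal upset, sweating, tremor, restlessness, yawning, pupil size, anxiety or irritability, arthralgias, piloerection of skin, and runny nose or tearing", and several have no direct counterpart on the list. A reader might infer that the list must be extended to match. That would be a preference and not a correction, since COWS already records these signs directly.

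**Conclusion.** The point holds in limited form. On the readable rows, 0 of 22 distinct terms is a withdrawal diagnosis. A post-dose event recorded only as opioid withdrawal, as Protocol 10.1.6 asks, therefore drops out of the withdrawal summary in SAP 8.7.1, while a single non-specific symptom enters it. The conclusion rests on two conditions: that no diagnosis term stands after Nervousness in the full appendix, and that the subject has no other listed event after the last dose.

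A reader might also infer that reported withdrawal is biased downward, or that a stated fraction of cases is lost. Neither follows. The share recorded as the diagnosis is unknown, and unrelated symptoms push the total the other way. What is established is a mismatch between the label of the row and what it counts, confined to that summary.

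**What to change.** - Check the complete appendix list. If no withdrawal diagnosis is on it, add the preferred term or terms to which a diagnosis of drug or opioid withdrawal codes in the MedDRA version used.
- Report two rows: (a) subjects with a withdrawal diagnosis; (b) subjects with listed symptom terms only, after the last dose.
- State whether the after-last-dose rule applies to row (a). A diagnosis made during treatment, including one that leads to stopping, is otherwise left undefined.
- Repair the cross-reference in SAP 8.7.1 so that it points to this list.

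The cost is a short SAP edit and one extra table row, with no new data. The reported incidence of withdrawal adverse events may rise as a result.

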Study Design:	
Open-label, multicenter, safety and tolerability study of NKTR-181 in the treatment of moderate to severe chronic low back pain or chronic noncancer pain.
 
The study will be divided into the following 3 periods:
 
 Screening: Up to 21 days Treatment: Up to 52 weeks (inclusive of a 1-week taper) Follow-up: Approximately 14 days after last dose of study drug

Test Product, Dose and Mode of Administration:	
Name: NKTR-181 tablet(s)
 
Dose, Route, and Frequency: NKTR-181 100-mg and 200-mg tablets will be administered orally twice daily (BID) as doses of 100 mg, 200 mg, 300 mg, 400 mg, 500 mg and 600 mg BID. Each dose will consist of tablets as follows:
 
100-mg dose = 1 x 100-mg tablet
 
200-mg dose = 1 x 200-mg tablet
 
300-mg dose = 1 x 200-mg tablet + 1 x 100-mg tablet
 
400-mg dose = 2 x 200-mg tablets
 
500-mg dose = 2 x 200-mg tablet + 1x 100-mg tablet
 
600-mg dose = 3 x 200 mg tablet
 
Subjects should take NKTR-181 BID at approximately 8 AM and 8 PM.

Safety:	
Key Safety Endpoints:
 
Safety and tolerability will be evaluated based on the following:
 
 • Incidence, type, seriousness, and severity of adverse events (AEs) reported • Clinical laboratory evaluations • Electrocardiograms (ECGs) • Vital signs (respiratory rate, pulse, heart rate, blood pressure, and temperature) • Drug withdrawal as measured by the Clinical Opiate Withdrawal Scale (COWS) and the Subjective Opiate Withdrawal Scale (SOWS) • Incidence of aberrant drug behavior according to MADDERS™ assessment • Suicidality assessment (Columbia-Suicide Severity Rating Scale [C-SSRS])
Efficacy:	
Efficacy Endpoint:
 
 • Efficacy will be evaluated based on the mBPI-SF administered at clinic visits.
Pharmacokinetics:	
Plasma concentrations of NKTR-181 and selected metabolites will be tabulated by time and subject and assessed for relationship to dose during the treatment phase. These data will be pooled with those from other studies during population PK analyses and investigation of exposure-response relationships for efficacy and safety.

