11.2 Determination of Sample Size

Approximately 600 subjects are expected to be enrolled (dosed). This number may increase or decrease to meet the International Conference on Harmonisation (ICH) regulatory exposure requirements for NKTR-181.

No formal sample size calculation will be performed for this long-term safety study. The sample size determination is based on the regulatory exposure requirement (ICH E1 A [1995]) that at least 300 subjects must complete 6 months (26 weeks) of NKTR-181 treatment and at least 100 subjects must complete 12 months (52 weeks) of NKTR-181 treatment.

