The duration of AEs will be calculated, partial dates for AE start, will be imputed as follows: If AE start date is missing, the missing day will be imputed as the first day of the month if the month of AE occurrence is after the month of first dose date. If the month of AE occurrence is the same month as first dose then the missing day will be imputed as the same day as the first dose date. If the month of AE occurrence is not the same as the month of first dose date then the missing day will be imputed as the first day of the month. If AE start month is missing and AE start year is the same as the year of the first dose, the missing month will be imputed as the month of the first dose date. If AE start year is not the same as the first dose year, the missing month and day of AE occurrence will be imputed as January 1 of the year. If AE start year is missing, no imputation will be done. If there is insufficient data for AE start date to make this comparison, the AE will be considered as treatment-emergent.

Partial dates for AE stop date will be imputed as follows: if the day and month are both missing, the missing date will be imputed as the treatment termination date or 14 days after last dose of study drug whichever is later. If only the day is missing but month and year are present, the missing day will be imputed as the last day of the month. No imputation will be done if the year is missing. For unresolved/resolving/unknown AEs with a completely missing stop date, there will be no imputation.

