8.10 Handling Missing Values

No other missing data imputation will be performed unless otherwise stated in this document.

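### The AE stop-date rule for a missing day and month ignores the recorded year, so the imputed date can fall in a different year and misstate AE duration

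*SAP*

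**What the plan says.** SAP section 8.7.1 sets separate rules for partial AE start and stop dates and states their purpose: "The duration of AEs will be calculated". For stop dates:

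- Day and month both missing: "the missing date will be imputed as the treatment termination date or 14 days after last dose of study drug whichever is later".
- Only the day missing: "the missing day will be imputed as the last day of the month".
- Year missing: "No imputation will be done if the year is missing".
- An event with no stop date at all, and an outcome of unresolved, resolving or unknown, also gets no imputation.

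The first rule can therefore operate only when a stop year has been recorded, yet nothing in it refers to that year. SAP section 8.10 closes off any other source of a limit: "No other missing data imputation will be performed unless otherwise stated in this document". Protocol section 1.0 sets treatment at up to 52 weeks, including a one-week taper.

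**The concern.** An imputed date should agree with the parts of the date that were recorded. The neighbouring rules do this. The day-only stop rule stays in the recorded month. The start-date rules compare the recorded year with the first-dose year, and the branch beginning "If AE start year is not the same as the first dose year" goes to 1 January of the recorded year. The rule for a missing stop day and month is the exception: it returns one fixed date per subject, whatever year the site entered.

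With treatment of up to a year, the recorded stop year and the year of that fixed date can easily differ. An event known to have ended in one year would then carry a stop date in another, and the duration derived from it would be impossible on the record. In a study whose primary objective is long-term safety, AE dates that contradict the eCRF should not be built in by the analysis plan.

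**Working it through.** No stated figure needs reproducing: Protocol section 11.2 says "No formal sample size calculation will be performed for this long-term safety study", and the SAP attaches no number to this rule. The check is date arithmetic.

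**Inputs**
- Reference date R = later of treatment termination and last dose + 14 days (SAP 8.7.1). I assume that termination is no later than last dose + 14, so R = last dose + 14.
- Treatment length L up to 364 days (52 weeks, Protocol 1.0). Last dose = first dose + L − 1.
- Duration = stop − start + 1. This is assumed, as the SAP gives no formula; the differences below do not depend on the + 1.
- Calendar dates are illustrative. First-dose days are taken as uniform over a 365-day year.

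**Step 1. How often R leaves the first-dose year.**
R = first dose + (L − 1) + 14 = first dose + L + 13. If r days remain from first dose to 31 December (r = 0 to 364), R crosses the year end when r < L + 13. That is L + 13 of the 365 possible first-dose days, up to all 365.

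| L (days) | First-dose days that cross | Share |
|---|---|---|
| 30 | 43 of 365 | 12% |
| 91 | 104 of 365 | 28% |
| 182 | 195 of 365 | 53% |
| 273 | 286 of 365 | 78% |
| 364 | 365 of 365 | 100% |

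These are shares of first-dose days, not of AE records.

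**Step 2. How far past the recorded year, for a completer.**
With L = 364 and a recorded stop year equal to the first-dose year, the excess past 31 December is 377 − r days. First dose on 1 January (r = 364) gives 13 days; first dose on 31 December (r = 0) gives 377; the mean is 195.

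**Step 3. Examples where R is too late.**
- First dose 1 Jul 2015, last dose 28 Jun 2016, AE start 1 Aug 2015, recorded stop year 2015. The rule gives 12 Jul 2016, a duration of 347 days. The latest date consistent with the record, 31 Dec 2015, gives 153 days. Excess: 347 − 153 = 194 days.
- Last dose 30 Sep 2017, recorded stop year 2016. The rule gives 14 Oct 2017. From 31 Dec 2016 to 30 Sep 2017 is 273 days, and 273 + 14 = 287 days past the latest possible date.

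**Step 4. Example where R is too early.**
Protocol 10.1.8 follows SAEs to resolution or stabilization with no day limit. Take last dose 10 Dec 2017 and recorded stop year 2018. The rule gives 24 Dec 2017, 8 days before the earliest date that the record allows (1 Jan 2018), so duration is understated by at least 8 days.

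**Step 5. Which direction is usual.**
If the event really ended on or before R, its recorded year cannot be later than R's year, so any contradiction puts the imputed date too late. The opposite error needs an event that ended after R and in a later calendar year. AE reporting runs to the end-of-study visit about 14 days after last dose (Protocol 10.1.2 and the Schedule of Assessments), so that class is narrower and consists mainly of SAEs under follow-up.

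**The case against.** **A late stop date is a convention.** Taking the latest plausible date is a recognised conservative choice, and the day-only rule makes it too. This stands: long imputed durations are not in themselves a fault. But a conservative rule chooses the latest date that fits the record, and this one can go past it. Only the contradiction with the recorded year is an error.

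**Another reading is possible.** One could keep the recorded year and take only the day and month from the reference date. The wording refers to the whole date, so this is less natural. It also fails: in the first example of step 3 it gives 12 Jul 2015, before the AE began on 1 Aug 2015.

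**Little depends on it.** The AE outputs named in SAP 8.7.1 and Protocol 11.9.3 are counts, percentages, severity, causality and event rates. No duration table is named. Protocol 10.1.2 asks for the resolution date of every AE, and visits are about monthly through most of treatment, so a known year with an unknown month should be uncommon and might never occur. This stands and limits the weight of the point.

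**Stronger readings that the documents do not support.** A reader might infer that the error always lengthens duration; step 4 shows that it can shorten it. A reader might infer that most subjects span two calendar years. The documents do not say so: crossing is certain only for completers, and Protocol 11.2 requires at least 300 subjects at 26 weeks and 100 at 52 weeks out of about 600. A reader might also infer that TEAE incidence is distorted; the definition in SAP 8.7.1 turns on onset or worsening after first dose, not on the stop date.

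**Conclusion.** The rule is wrong as written, and the consequence is small. When only the stop year is known, it can return a date in a different year from the one recorded, and no other section prevents this. The usual error is a date that is too late: for a 364-day completer with a recorded stop year equal to the first-dose year it is certain, at 13 to 377 days past 31 December. The upper end needs a first dose at the very end of December. A date that is too early is possible for events that end in a year after last dose + 14 days.

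The effect is confined to AE duration. The number of affected records is not given and could be zero. The sizes rest on the assumptions listed with the check: termination no later than last dose + 14 days, uniform first-dose days and a 365-day year.

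**What to change.** Keep the reference date R and bound it to the recorded stop year Y. In SAP 8.7.1, state that when day and month are missing the imputed stop date is R, except that:

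- if R is after 31 December of Y, use 31 December of Y;
- if R is before 1 January of Y, use 1 January of Y;
- the result is never earlier than the AE start date.

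As a formula: stop = max(AE start, min(31 Dec Y, max(1 Jan Y, R))).

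In the worked examples this gives 31 Dec 2015 (duration 153 days rather than 347), 31 Dec 2016 rather than 14 Oct 2017, and, if that AE began by then, 1 Jan 2018 rather than 24 Dec 2017. An upper cap alone would not be enough, because the last case would still contradict the record.

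The cost is one SAP sentence and a small change to the date-derivation code. No data collection or other analysis changes.
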